6.2 STUDY RATIONALE

Commonly, mM patients with CNS involvement are excluded from clinical trials (21). Hence, no information from interventional clinical trials on activity of combined targeted therapy (BRAFi/MEKi) is available until present. Additionally, the pivotal study of combined vemurafenib and cobimetinib treatment coBRIM has not included mM patients with brain metastases. Currently, there is one phase II trial (CONVERGE) for

the treatment of brain metastases with vemurafenib and cobimetinib under investigation (22). The primary endpoint of this study is intracranial response. Radiological or stereotactical treatment of brain metastases is only allowed prior to treatment start. CONVERCE evaluates the efficacy of vemurafenib and cobimetinib in brain metastases in a highly controlled setting.

To date no data are available on effectiveness, safety and, utilization of cobimetinib / vemurafenib in patients with mM in daily clinical routine in Germany

For information on the condition under observation please refer to the most recent version of the SmPC.

For information on vemurafenib /cobimetinib please refer to the most recent version of the SmPCs.

7. RESEARCH QUESTION AND OBJECTIVES

7.1 RESEARCH QUESTION

The aim of this multi-center, non-interventional study is to provide data on effectiveness of cobimetinib plus vemurafenib with a special focus on OS, safety and utilization of the combination therapy in two different cohorts: patients with unresectable or metastatic BRAF V600-mutated malignant melanoma with or without cerebral metastases.

7.2 OBJECTIVES

The primary objective for this study is as follows:

- to estimate OS according to cohorts with cerebral and without cerebral metastases (investigator assessed)

The secondary objectives for this study are as follows:

- to estimate intermediate endpoints, including:
 - PFS (investigator assessed)
 - ORR (CR + PR) (investigator assessed)
 - Intracranial ORR (iORR)
 - Extracranial ORR (eORR)
 - Time to CNS relapse in cohort with cerebral metastases / development of cerebral metastases in cohort with solely extracerebral metastases (investigator

assessed)

- to describe clinical characteristics of patients overall, and according to both cohorts (i.e. demographic data, medical history, information on primary mM, ECOG performance status, serum LDH at baseline, number of extracranial metastatic sites at baseline; in case of brain metastasis: number of brain metastases, largest diameter, symptomatic/asymptomatic brain metastasis, leptomeningeal disease, concomitant therapy for brain metastasis)
- to describe utilization of cobimetinib / vemurafenib (type and number of previous adjuvant and palliative treatments, dosing schedules, treatment beyond progression, reason for discontinuation, subsequent therapies and concomitant medication)
- to describe utilization of cobimetinib / vemurafenib and treatment for brain metastasis (prior local treatment for brain metastases, concomitant radiotherapy or surgery, type of radiotherapy, steroid use prophylactic or therapeutic, use of anticonvulsiva)
- to describe patient reported outcome using the EORTC QLQ-C30 questionnaire

Safety Objectives

The safety objectives for this study are as follows:

The incidence of all adverse events (AEs) and serious adverse events (SAEs) in cobimetinib / vemurafenib treated patients.

- All protocol-specified adverse events (AEs) described in this section will be reported and graded according to the National Cancer Institute Common Terminology Criteria for Adverse Events version 4 (CTCAE v4.03).
- Incidence and outcomes of serious and non-serious AEs of interest (i.e., those AEs identified by Genentech/Roche as potential or known risks of cobimetinib and/or vemurafenib use)
- These AEs of interest for the combination of vemurafenib and cobimetinib include the following:
 - Any grade serous retinopathy
 - Any grade retinal vein occlusion
 - Grade \geq 2 left ventricular dysfunction

- Rhabdomyolysis grade ≥ 3 CPK elevation (including elevations of CPK-MM in conjunction with other laboratory evidence (aldolase and urine myoglobin), clinical features consistent with rhabdomyolysis such as muscle pain, sings or renal failure, or dark red or brown urine)
- Grade ≥ 3 hemorrhage event or any grade cerebral hemorrhage
- Grade ≥ 3 rash
- Grade ≥ 3 photosensitivity
- Events suggestive of drug induced liver injury or other Grade ≥ 3 hepatotoxicity as defined by:
 - o Grade ≥ 3 elevations of aspartate aminotransferase (AST), alanine aminotransferase (ALT), serum bilirubin, gamma-glutamyl transpeptidase/transferase (GGT), OR cases of elevated ALT or AST in combination with either an elevated bilirubin or clinical jaundice
- AE potentially associated with prolongation of cardiac repolarization
- New or progression of RAS mutant malignancy, cutaneous squamous cell carcinoma, new primary melanoma, or basal cell carcinoma, or other new malignancies.

8. RESEARCH METHODS

8.1 STUDY DESIGN

[figure not shown]
This multi-center, two cohort non-interventional study does not influence the individually selected treatment scheme. The physicians' choice for a particular type of therapy is not influenced. Only documentation of the chosen therapy is part of this study. Data collection during therapy with cobimetinib / vemurafenib should reflect clinical routine. Overall, the duration of patient inclusion will last until end of Q4 2018.

- Patients with:

Cohort A: 157 patients with AJCC stage IIIC unresectable and stage IVA, B, C mM without cerebral metastases

or

Cohort B: 68 patients with AJCC stage IVC and cerebral metastases may be included

Start Date of Study:

The study start date will be the date of the first data collection: the date from which information on the first study subject is recorded in the study database. The planned start date is Q2/2017.

End of Study:

The end of the study will be the date from which the last information of the last subject is recorded in the study database. The planned end of study date is Q2/2020.

Length of Study

This study will last for 3 years. Patients will be recruited for 18 months and followed up to 18 months.

A data collection overview is provided in Appendix 2.

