- These AEs of interest for the combination of vemurafenib and cobimetinib include the following:
 - Any grade serous retinopathy
 - Any grade retinal vein occlusion
 - Grade ≥ 2 left ventricular dysfunction
 - Rhabdomyolysis grade ≥ 3 CPK elevation (including elevations of CPK-MM in conjunction with other laboratory evidence (aldolase and urine myoglobin), clinical features consistent with rhabdomyolysis such as muscle pain, sings or renal failure, or dark red or brown urine)
 - Grade ≥ 3 hemorrhage event or any grade cerebral hemorrhage
 - Grade ≥ 3 rash
 - Grade ≥ 3 photosensitivity
 - Events suggestive of drug induced liver injury or other Grade ≥ 3 hepatotoxicity as defined by:
 - Grade ≥ 3 elevations of aspartate aminotransferase (AST), alanine aminotransferase (ALT), serum bilirubin, gamma-glutamyl transpeptidase/transferase (GGT), OR cases of elevated ALT or AST in combination with either an elevated bilirubin or clinical jaundice

- AE potentially associated with prolongation of cardiac repolarization
- New or progression of RAS mutant malignancy, cutaneous squamous cell carcinoma, new primary melanoma, or basal cell carcinoma, or other new malignancies.

Study Design

This multi-center, two cohort non-interventional study does not influence the individually selected treatment scheme. The physicians' choice for a particular type of therapy is not influenced. Only documentation of the chosen therapy is part of this study. Data collection during therapy with cobimetinib / vemurafenib should reflect clinical routine. Overall, the duration of patient inclusion will last until end of Q4 2018.

- Patients with:

Cohort A: 157 patients with AJCC stage IIIC unresectable and stage IVa, b, c mM without cerebral metastases

or

Cohort B: 68 patients with AJCC stage IVc and cerebral metastases

may be included

Description of Study

This prospective multi-center non-interventional study will include patients with an underlying diagnosis of BRAF V600 mutated unresectable or metastatic malignant melanoma, either with or without cerebral metastases. Data collection during therapy with Cobimetinib / Vemurafenib should reflect clinical routine. Study duration will be three years. Data from individual patients will be documented up to three years.

Population

Patients must meet the following criteria for study entry:

- Adult patients with unresectable or metastatic melanoma with a BRAF V600 mutation according to SmPC

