8.5 STUDY SIZE

In this study 225 patients will be enrolled across 40 sites.

The following rates are expected for the two different populations:

- Cohort A: patients with AJCC stage IIIC unresectable and stage IVa, b, c mM without cerebral metastases: 70% (157 patients)
- Cohort B: patients with AJCC stage IVC and cerebral metastases: 30% (68 patients)

The required sample size was estimated for Cohort B (brain metastases) and Cohort A (non-brain metastases). For the brain metastases group, a historical median OS of about 8 months is assumed under vemurafenib treatment (1-4). The aim was to find the required number of patients in order to estimate the median OS in such a way that the lower limit of the 95% confidence interval is at least 8 months. If a median OS of 12 months is assumed, a one-sample non-parametric survival analysis would yield in a confidence interval of [8.5 months ; 15.5 months], given the sample size was 68 (10% dropout rate included). For the non-brain metastases group, the aim was to set the number of patients in such a manner that the lower boundary of its associated median OS confidence interval does not overlap with the upper boundary of the brain metastasis group. If a median OS of 25 months is assumed, the 95% confidence interval for the median OS is [19; 31] months (5).

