8.7.1 Safety Analyses

All patients who received at least once cobimetinib and vemurafenib will be part of the safety population which is identical to the core analysis population.

The analysis of safety outcomes/variables is based on the incidence and severity of all AEs, SAEs, AEs with NCI CTCAE version {4.0}.

Safety will be assessed through summaries of adverse events. Descriptive statistics will be used to summarize all safety data. Adverse event data will be reported in listings and presented in frequency tables by Medical Dictionary for Regulatory Affairs (MedDRA) terms. All adverse events occurring after treatment will be summarized. Summaries of adverse events by grade, seriousness, and relationship to study treatment will be presented, as well as summaries of adverse events leading to death or to premature withdrawal from study treatment. Serious adverse events, including deaths, will be listed separately and summarized.

8.7.2 Effectiveness Analyses Effectiveness analyses will be based on all enrolled patients according to both defined cohorts:

Patients with:

Cohort A: patients with AJCC stage IIIC unresectable and stage IVA, B, C mM without cerebral metastases

or

Cohort B: patients with AJCC stage IVC and cerebral metastases

All effectiveness and variables documented in this study will be analyzed by means of descriptive analyses.

Continuous data will be summarized using mean, standard deviation, median, minimum and maximum. Categorical variables will be expressed as absolute and relative number and 95% CI. Kaplan-Meier estimates and Cox-regression will be used to model data on time to disease progression and OS.

All efficacy analyses will be performed separately for both groups.

The primary variable OS is defined as time interval from study start to death for any cause. Patients who have not died will be censored at the last date the patient was known to be alive. A 95% confidence interval will be calculated for the median overall survival.

PFS is defined as the interval between the start date of treatment and the date of progression or death for any cause, whichever comes first. Patients who have neither progressed nor died will be censored on the date of last evaluable tumor assessment.

Patients who had no post-baseline assessments and did not have an event will be censored OR is defined as a complete or a partial response documentation on the basis of investigator assessment.

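### The Cohort A planning interval of [19; 31] months ignores administrative censoring, so its upper limit will often not be reached; the follow-up sentence should also be reworded so that it cannot be read as an 18-month cap per patient

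*Protocol*

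**What the plan says.** Protocol section 8.5 sizes Cohort A so that the lower limit of its median OS interval lies above Cohort B's upper limit, stated as 15.5 months. It then says: "If a median OS of 25 months is assumed, the 95% confidence interval for the median OS is [19; 31] months". The section gives no recruitment pattern, length of follow-up or allowance for patients still alive at study end.

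The calendar is in section 8.1 and repeated in the Synopsis: "The planned start date is Q2/2017", "The planned end of study date is Q2/2020" and "Overall, the duration of patient inclusion will last until end of Q4 2018". Under Length of Study the text reads "This study will last for 3 years" and then "Patients will be recruited for 18 months and followed up to 18 months". The Synopsis, under Description of Study, says "Data from individual patients will be documented up to three years".

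In section 8.7.2 survivors are censored when last known alive, and "A 95% confidence interval will be calculated for the median overall survival". Sections 8.7 and 8.7.2 also name Kaplan-Meier estimates and Cox regression for OS.

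**The concern.** OS by cohort is the primary objective, and [19; 31] is the only precision figure given for Cohort A, which is about 70% of the sample (157 of 225). A planned median of 25 months with an upper limit of 31 needs many patients observed around and beyond 31 months. In a three-year study that recruits for half its length, few are. If the interval was computed without censoring, 8.5 promises a precision that the design does not deliver.

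The follow-up sentence adds a second risk. It does not say what the second 18 months is counted from. A site that took it as 18 months per patient would stop collecting survival data well before the planned median, and data not collected then may be hard to recover.

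**Working it through.** **Inputs.** From 8.5: median 25 months, interval [19; 31], n = 157, and a 10% dropout. The dropout is stated for Cohort B only; carrying it to Cohort A is an assumption and gives 157 × 0.9 = 141. From 8.1: 18 months of recruitment and a three-year study. Also assumed: exponential survival and uniform recruitment.

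**1. Reproducing the stated interval.** With no censoring, the large-sample non-parametric interval is m ± 1.96·m/(ln 2·√n).

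- n = 141: 25 ± 49/(0.693 × 11.87) = 25 ± 5.95, giving [19.05; 30.95].
- n = 157: 25 ± 49/(0.693 × 12.53) = 25 ± 5.64, giving [19.4; 30.6].

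So [19; 31] is the uncensored result with n = 141.

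**2. What the calendar provides.** With 18 months of recruitment in 36 months, follow-up ranges from 18 to 36 months.

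- The expected proportion who die is 1 − (0.607 − 0.369)/(18 × ln 2/25) = 0.52. That is about 82 deaths of 157 (74 of 141); the formula in step 1 assumes that all patients die.
- At 31 months survival is 0.5^(31/25) = 0.423, and only patients enrolled in the first 5 of 18 months can still be under observation. The number at risk is about 157 × 5/18 × 0.423 = 18 (17 with n = 141).

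**3. Simulated Kaplan-Meier median with Brookmeyer-Crowley log-log limits.** Several thousand cohorts per scenario, n = 157 and 141:

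| Follow-up per patient | Median reached | Upper limit not reached |
|---|---|---|
| 18–36 months (18 + 18) | about 98% | about 42–46% |
| 15–36 months (21 months' recruitment, 36-month study) | not tabulated | about 48–51% |
| 18–39 months (21 + 18, longest calendar reading) | over 99% | about 23–28% |
| 36 months for everyone | about 100% | about 8–9% |

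In the 18–36 month case the upper limit is at or below 31 months in only about 35–39% of trials. The lower limit is typically 19 to 20 months and exceeds 15.5 in about 95%. Log-transformed limits are less favourable, with the upper limit missing in 60–65%. The last row shows that 36 months on every patient would typically give an upper limit near 31, but recruitment over 18 months of a three-year study rules that out.

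**4. The literal 18-month cap.** S(18) = 0.5^(18/25) = 0.607, so about 62 of 157 would have died. Without earlier losses, the curve reaches 0.50 only if at most half survive to 18 months:

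- P(Bin(141, 0.607) ≤ 70) = 0.5%.
- P(Bin(157, 0.607) ≤ 78) = 0.3%.

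With a median of 22.3 months, the figure section 6.1 quotes for the combination, the chance is about 4%.

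**The case against.** The strongest reply is that no cap was intended. The sentence stands under Length of Study, directly after the statement that the study lasts three years, and 18 + 18 = 36 months. Read as study phases, it fits the start and end dates and the Synopsis maximum of three years, which is what the first patient enrolled would have. The OS censoring rule has no 18-month truncation, and no section tells a site to close a patient at 18 months. This largely stands. A reader might infer that the Cohort A median cannot be estimated, but that follows only from the less coherent reading. What remains is that the sentence does not say what follow-up is counted from, and sections 8.4.3 and 10.1.2.1 refer to an observation period without giving its length.

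A reader might also infer that the primary objective would have no answer for Cohort A because only the median is planned. The protocol does not support this: Kaplan-Meier estimates and Cox regression are named for OS, and a curve would be reported even under a cap. Fixed-time survival rates are ordinary SAP content, so their absence here is no finding.

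Nor does the open upper limit defeat the stated Cohort A aim. That aim concerns the lower limit, which holds. The study is descriptive with no formal testing, so [19; 31] is a planning figure and not a success criterion. That limits the consequence but does not make the figure right.

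Finally, letting follow-up run from 15 to 33 months leaves the upper limit unreached in about 72% of trials. That implies a 33-month study and contradicts the stated three years; with 36 months and a 15-month minimum the figure is 48–51%.

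**Conclusion.** The point holds in a limited form. The Cohort A interval in 8.5 is an uncensored calculation. Under the planned 18–36 months of follow-up, the median is estimable in about 98% of trials and the lower limit behaves as planned. The upper limit is missing in about 42–46% (23–28% to 48–51% across calendars compatible with the document) and is at or below 31 months in little more than a third.

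The follow-up sentence is ambiguous rather than plainly contradictory. Its likely meaning is 18 months after the last enrolment. Taken literally as a cap, it conflicts with the Synopsis and leaves the Cohort A median unreached in over 99% of trials.

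The sizes rest on exponential survival with a median of 25 months, uniform recruitment and 141 to 157 patients. The roughly 95% for the lower-limit aim compares with Cohort B's stated 15.5 as a fixed value; in simulation Cohort B's own upper limit was typically 16 to 18 months. Under the cap, the main conclusion does not depend on the exponential form: if the true median is 25 months, more than half of patients are alive at 18 months.

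**What to change.** 1. In section 8.1 and in the Synopsis, replace the follow-up sentence with a statement that every patient is followed for survival from start of treatment until death, withdrawal of consent or the common study end (Q2/2020), whether or not still on treatment. Keep the three-year figure as the maximum for the earliest patients.
2. In section 8.5, restate the Cohort A precision allowing for administrative censoring: lower limit about 19 months, upper limit may not be reached by study end. Give the recruitment and follow-up assumptions behind it.

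The cost is protocol wording in three places. It needs no additional patients and no longer study, and survival follow-up stays within the planned calendar.

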8.1.1 Rationale for Study Design**8.2 SETTING****8.2.1 Centers**

This study will be conducted at approximately 40 centers in one country (Germany).

Additional centers may be added or substituted if the ones stated above are underperforming.

8.2.2 Study Population

Patients receiving treatment for BRAF V600-mutated unresectable or metastatic mM with a combination of vemurafenib and cobimetinib according to standard of care and in line with the current summary of product characteristics (SmPC)/local labeling and who have no contraindication to a treatment with a combination of vemurafenib and cobimetinib therapy as per the local label are eligible for observation in this non interventional study if the following criteria applies.

Patients must meet the following criteria for study entry:

- Adult patients with unresectable or metastatic melanoma with a BRAF V600 mutation according to SmPC
- Be willing and able to provide informed consent for the non-interventional study.
- Male or female patient being ≥ 18 years of age on day of signing informed consent.
- Histologically confirmed diagnosis of unresectable or metastatic mM (according to the cobimetinib label)
- Presence of BRAF mutation (V600) in tumor tissue prior to enrolment.

Patients who meet any of the following criteria will be excluded from study entry:

- Previous treatment with BRAF- and/or MEK inhibitors prior to study entry
- Hypersensitivity to the active substances or to any of the excipients listed in appendix 4.

Patient selection criteria are as broad as mentioned in the SmPC, with one exception: Patients previously treated with BRAF- and/or MEK inhibitors are excluded. This may lower the number of patients available for recruitment in a further line setting.

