8.3 VARIABLES

8.3.1 Primary Variable

The primary variable for this study is as follows:

- OS: Time interval between start of treatment and date of death for any cause

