9.3 INFORMED CONSENT

The marketing authorization holder's sample Informed Consent Form (and ancillary sample Informed Consent Forms such as a Child's Assent or Caregiver's Informed Consent Form, if applicable) will be provided to each site. If applicable, it will be provided in a certified translation of the local language. The marketing authorization holder must review and approve any proposed deviations from the marketing authorization holder's sample Informed Consent Forms or any alternate Consent Forms proposed by the site (collectively, the "Consent Forms") before IRB/EC submission. The final Consent Forms approved by the IRB/EC must be provided to the marketing authorization holder for health authority submission purposes according to local requirements.

The Consent Forms must be signed and dated by the patient or the patient's legally authorized representative before start of documentation of his or her data in the CRF.

The case history or clinical records for each patient shall document the informed consent process and that written informed consent was obtained prior to first documentation of this patient's data in the CRF.

By signing the form, the patient confirms that he/she has been informed about the study and agrees to pseudonymous data collection, pooling of data with similar scientific data

(if applicable), and the possibility of monitoring activities. It is the responsibility of the physician to obtain written informed consent from each patient participating in the study, after adequate explanation of the aims, methods, anticipated benefits, and potential hazards of the study. The physician must also explain that the patient is completely free to refuse to enter the study or to withdraw from it at any time, for any reason and without losing the benefit of any medical care to which the patient is entitled or is presently receiving.

A copy of each signed Consent Form must be provided to the patient or the patient's legally authorized representative. All signed and dated Consent Forms must remain in each patient's study file or in the site file and must be available for verification by Site Operations Representative at any time.

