10.1.2.1 Adverse Event Reporting Period

Physicians will seek information on AEs at each patient contact. All AEs subject to the collecting and reporting requirements outlined in this protocol, whether reported by the

patient or noted by study personnel, will be recorded in the patient's medical record and in the AE section of the CRF.

Once the patient is enrolled in the study, AEs will be collected until the end of his or her observation period. After this period, the physician is not required to actively monitor patients for AEs but if the treating physician becomes aware of any related AEs to any medicinal product they should be notified to the competent authority in the Member State where the reactions occurred or to the marketing authorization holder of the suspected medicinal product, but not to both (to avoid duplicate reporting).

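### Section 8.2.2 does not settle whether patients already on the combination may enrol; if they do, OS counted from treatment start may be overstated and early adverse events missed

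*Protocol*

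**What the plan says.** **Who may enter.** Section 8.2.2 opens the study to "Patients receiving treatment for BRAF V600-mutated unresectable or metastatic mM with a combination of vemurafenib and cobimetinib according to standard of care". Among its exclusions is "Previous treatment with BRAF- and/or MEK inhibitors prior to study entry", repeated in the synopsis and in footnote a of Appendix 2. Section 8.2.2 then comments on the exclusion: "This may lower the number of patients available for recruitment in a further line setting".

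**When consent is given.** Section 9.3 requires the form to be signed "before start of documentation of his or her data in the CRF". No section states an interval between first dose and enrolment.

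**Where the clock starts.** Section 8.3.1 has "OS: Time interval between start of treatment and date of death for any cause". Section 8.7.2 has "The primary variable OS is defined as time interval from study start to death for any cause", and section 8.1 fixes that term for the study as a whole: "The study start date will be the date of the first data collection". PFS and time to CNS relapse (both 8.7.2) run from the start of treatment.

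**When adverse events are collected.** Section 10.1.2.1: "Once the patient is enrolled in the study, AEs will be collected until the end of his or her observation period". Appendix 2 has no adverse event entry in the baseline column.

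**The concern.** The eligibility sentence and the exclusion pull against each other. If the exclusion covers the current course, nobody already dosed can enter. If it covers only earlier lines, as the remark about the further-line setting suggests, a patient can enter weeks or months after first dose. About 40 sites could apply the rule differently.

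Under the second reading, a patient must have survived from first dose to enrolment in order to be in the data. Patients who die early are never enrolled, yet the OS clock credits the enrolled with the time before entry. Median OS then tends upwards. The effect is relatively largest in Cohort B, where survival is shortest and where section 8.5 aims for a lower 95% limit of at least 8 months, with a projected limit of 8.5. Adverse events between first dose and enrolment would also be absent, which lowers early incidence.

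**Working it through.** **1. The plan's own figures.** Inputs from 8.1 and 8.5: Cohort B median 12 months and N = 68, Cohort A median 25 months and N = 157, 10% dropout, 18 months of accrual plus 18 months of follow-up. Section 8.5 names the dropout only for Cohort B; applying it to A as well is an assumption. Assume exponential survival with rate r = ln2/m and uniform accrual. The event probability is p = 1 − [e^(−18r) − e^(−36r)]/(18r), and the interval is m ± 1.96·m/√events.

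- Cohort B: 0.9 × 68 = 61.2 patients; p = 0.780; 47.7 events; 12 ± 3.4 = [8.6; 15.4], against the stated [8.5; 15.5].
- Cohort A: 0.9 × 157 = 141.3 patients; p = 0.522; 73.8 events; 25 ± 5.7 = [19.3; 30.7], against the stated [19; 31].

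The planning intervals reproduce approximately. They presuppose that everyone is observed from the OS origin and say nothing about entry.

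**2. Naive median under late entry.** The protocol gives neither the share f of enrolled patients who enter late nor their delay D, so both are assumptions. A late entrant is alive at D by construction, so for t ≥ D the naive curve is

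S*(t) = (1 − f)·2^(−t/m) + f·2^(−(t − D)/m).

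Setting this to 0.5 gives a naive median of m·[1 + log2(1 − f + f·2^(D/m))].

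Example with m = 12, f = 0.5, D = 3: 2^(0.25) = 1.1892; 1 − 0.5 + 0.5 × 1.1892 = 1.0946; log2 = 0.1304; 12 × 1.1304 = 13.6 months.

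| Late share | Delay (months) | True 8 | True 12 | True 25 |
|---|---|---|---|---|
| 0 | – | 8.0 | 12.0 | 25.0 |
| 25% | 1 | 8.3 | 12.3 | 25.3 |
| 50% | 1 | 8.5 | 12.5 | 25.5 |
| 50% | 3 | 9.6 | 13.6 | 26.5 |
| 100% | 3 | 11.0 | 15.0 | 28.0 |

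For short delays the shift is roughly f × D.

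**3. Another shape of delay.** Let every treatment starter have a delay uniform on 0 to a months. The share alive at entry is (1 − 2^(−a/m))/(a·ln2/m), and the naive median is m·[1 − log2(that share)]. With m = 12:

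- a = 3: share 0.918 (8% die before entry), median 13.5.
- a = 6: share 0.845 (16% die before entry), median 14.9.

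**4. Effect on the Cohort B aim.** Kaplan-Meier simulation, N = 68, true median 8 months (no gain over the benchmark), 2,000 runs per setting. The chance that the lower 95% limit reaches 8 months is:

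- no late entry: about 2%
- 50% at 1 month: 4%
- 25% at 3 months: 6%
- 50% at 3 months: 20%
- 100% at 3 months: 68%

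**5. Does counting from enrolment repair it?** With patients at risk only from entry, the settings in which part of the cohort enters at first dose return to a median of about 8.0 and a chance of about 2%. If all enter at 3 months, the estimate stays at 10.9, because nobody is observed in the first three months.

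**The case against.** The exclusion, taken at its word and dated to study entry, keeps out anyone already dosed, and then there is no guaranteed time at all. The remark about further-line patients names a recruitment consequence and does not define the criterion. Other features suggest entry at or before first dose: the synopsis calls the study prospective, the core population requires at least one dose (redundant if enrolment normally follows dosing), and QLQ-C30 change is measured from a baseline. Handling of late entry is commonly left to the SAP, which is not shown. Section 8.9 already acknowledges selection bias and promises sensitivity analysis. Section 8.7 plans no formal hypothesis test, so no decision turns on the half-month between 8.5 and 8.

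Much of this stands. A reader might infer that enrolment is simply not tied to first dose and that median OS will therefore be inflated. The protocol does not support that: one of its two readings prevents the bias, and nothing shows that late entry is planned. The absence of a left-truncation rule is not a defect of the protocol either.

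A reader might also take OS from 8.3.1 alone. Section 8.7.2 uses a different origin. If patient enrolment was meant there, OS would lose the guaranteed time, although PFS and time to CNS relapse would still start at treatment. As 8.1 defines the term, however, it is one calendar date for the whole study and cannot serve as a patient's time zero.

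What the objection does not remove is the conflict within 8.2.2. A SAP can adjust an analysis, but it cannot tell sites whom to enrol, and step 5 shows that adjustment fails when all patients enter late.

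**Conclusion.** The point holds as an unresolved entry rule with a conditional consequence. Section 8.2.2 supports two incompatible readings, section 9.3 does not choose between them, and the OS origin differs between 8.3.1 and 8.7.2. If patients enrol after first dose and OS runs from treatment start without adjustment, the median is biased upwards. For a true Cohort B median of 12 months the shift runs from zero (no late entry), through about 0.3 to 0.5 months (25 to 50% at 1 month) and 1.6 months (50% at 3 months), to 3 months (all at 3 months). These figures assume exponential survival and rest on an assumed share and delay. They show what could happen and do not predict what will. Early adverse event incidence would be understated by an amount that the document does not allow to be calculated.

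**What to change.** 1. In 8.2.2 and 9.3, state that consent takes place on or before the day of first dose, and that the exclusion refers to BRAF or MEK inhibitors given before the current combination course. Carry the wording into the synopsis and Appendix 2.
2. Reconcile 8.3.1 and 8.7.2 so that OS has one origin, the patient's own treatment start.
3. If later enrolment is to be allowed, limit it to a short stated window and count patients at risk in the time-to-event analyses only from the consent date (left truncation). Consent date (Appendix 2, footnote a) and therapy start date (8.4.2) are already collected.

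The cost is protocol wording plus, under item 3, an entry time in the Kaplan-Meier and Cox programs. Items 1 and 2 may lose a few late-identified patients. Item 3 thins the early risk sets and makes early estimates less precise. With all delays uniform on 0 to 3 months and a median of 12, the share of enrolled patients under observation by 0.5 months is (1 − 2^(−0.5/12))/(1 − 2^(−3/12)) = 0.0285/0.1591 = 18%, about 12 of 68 in Cohort B. Left truncation does not recover the median if nearly all patients enter late, so the window should be short.
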